5. STATISTICAL ANALYSES OF PRIMARY SAFETY ENDPOINTS

Safety analysis will be performed on patients allocated to receive vaccination. The percentage of subjects with at least one local AEs with at least one general AE (solicited and unsolicited) and with any AE during the 7-day or total follow-up period up to 28 days after the last vaccine dose and overall will be tabulated with exact 95% CI. The percentage of doses followed by at least one local AE (solicited and unsolicited), by at least one general AE (solicited and unsolicited) and by any AE during the 7-day or the total follow up period up to 28 days after the last vaccine will be tabulated with exact 95% CI. The same computations will be done for Grade 3 AEs, for any AEs considered related to vaccination and for any Grade 3 AEs considered related to vaccination. The percentage of subjects reporting each individual solicited local AE (any grade and Grade 3) and solicited general AE (any grade, Grade 3, any related, Grade 3 related, resulting in medically attended visit) during the 7-day follow-up period (Day 0-6) after each vaccine dose and overall will be tabulated for each group. Similarly, the percentage of doses followed by each individual solicited local and general AE will be tabulated, overall vaccination course, with exact 95% CI. For fever, the number and percentage of subjects reporting fever by half degree (°C) cumulative increments during the first seven days (Day 0-6) after each vaccine dose and overall will be tabulated. Similar tabulations will be performed for any fever with a causal relationship to vaccination and Grade 3 ($> 39.5^{\circ}\text{C}$) causally related fever. The percentage of subjects reporting unsolicited AEs from the date of the first vaccine dose up to 28 days after the last vaccine dose will be tabulated by group and by MedDRA preferred term with exact 95% CI. Similar tabulation will be done for Grade 3 unsolicited AEs, for any causally related unsolicited AEs and for Grade 3 causally related unsolicited AEs. The percentage of subjects reporting SAEs and pregnancies will be described in detail. The percentage of vaccinated subjects reporting AEs of specific interest (meningitis and pIMDs) will be described in detail.

Thus, in summary, the safety analysis will be as follows:

- Frequency (%) of occurrence of solicited local and general AEs within seven days (day of vaccination and six subsequent days) after each vaccination with exact 95% CI by group and severity.
- Frequency (%) of occurrence of unsolicited AEs from the date of the first vaccination to 28 days after the last vaccination, according to the Medical Dictionary for Regulatory Activities (MedDRA) classification with exact 95% CI, by group and severity.
- Frequency (%) of occurrence of SAEs (all, fatal, related to investigational vaccine) within 28 days (day of vaccination and 28 subsequent days) after each vaccination, according to the MedDRA classification with 95% CI.
- Frequency (%) of occurrence of SAEs (all, fatal, related to investigational vaccine) during the whole study period according to the MedDRA classification with exact 95% CI.
- Frequency (%) of occurrence of AEs and SAEs leading to withdrawal from further vaccination from Dose 1 (Day 0) up to study conclusion (Day 180), according to the MedDRA classification, for each vaccinated subject exact 95% CI.
- Frequency (%) of occurrence of pIMDs from Dose 1 (Day 0) up to study conclusion (Day 180), according to MedDRA classification, for each vaccinated subject with exact 95% CI.
- Frequency (%) of occurrence of meningitis from Dose 1 (Day 0) up to study conclusion (Day 180), according to the MedDRA classification, for each vaccinated subject exact 95% CI.

These will be summarised in table 4 below:

Table 4 Safety analysis

Safety parameter	R21/Matrix-M™ + DHA-PIP + SLD-PQ n=X	R21/Matrix-M™ n=X	No Vaccine n=X
Solicited local and general AEs within seven days n(%), (95% CI)			
Unsolicited AEs: date of 1 st vaccine to 28 days after last vaccine n(%), (95% CI)			
SAEs within 30 days after each vaccine n (%), (95% CI)			
SAEs for whole period n (%), (95% CI)			
AEs+SAEs leading to withdrawal from further vaccination from Dose 1 to study conclusion n(%), (95% CI)			
pIMDs from Dose 1 to study conclusion n(%), (95% CI)			

Biochemistry and haematological safety assessment.

Biochemistry (ALT, AST and creatinine) and haematological (haemoglobin, WBC, and platelets) laboratory values will be presented according to toxicity grading scales and tabulated by group. The normal ranges and toxicity grading for laboratory safety parameters those will be used in this study are in Appendix section (Table A1):

The following definitions will be used for clinical adverse events in this report: The intensity should be assigned to one of the following categories:

1 (mild) = An AE which is easily tolerated by the subject, causing minimal discomfort and not interfering with everyday activities.

2 (moderate) = An AE which is sufficiently discomforting to interfere with normal everyday activities.

3 (severe) = An AE which prevents normal, everyday activities. In adults, such an AE would, for example, prevent attendance at work/school and would necessitate the administration of corrective therapy.

An AE that is assessed as Grade 3 (severe) will not be confused with a SAE. Grade 3 is a category used for rating the intensity of an event; and both AEs and SAEs can be assessed as Grade 3. A grade 3 AE may not necessarily be an SAE in this study.

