1.5 Assessment of Adverse Events and Serious Adverse Events

1.5.1 Assessment of intensity

The intensity of the following solicited AEs will be assessed as described:

Adverse Event	Parameter
Redness at injection site	Record greatest surface diameter in mm
Swelling at injection site	Record greatest surface diameter in mm
Bruising at injection site	Record greatest surface diameter in mm
Fever*	Record temperature in °C/°F
Other AEs	Record grading

**Research Proposal Submission Form
for a study involving human subject enrollment WITH
specimen collection**

Document No.: FTM ECF-033-01

Page 43 of 52

Severity grading criteria for the self-assessment for AEs.

GRADE 0	none
GRADE 1	noticeable, but no impact on activities
GRADE 2	noticeable and alters, but does not prevent daily activities
GRADE 3	prevents normal daily activities, and/or requires visits with a medical professional
GRADE 4	precipitates ER visit or hospitalization (these are, of course, also SAEs; Serious Adverse Effects).

*Fever is defined as temperature $\geq 37.5^{\circ}\text{C}$ / 99.5°F for oral, axillary or tympanic route, or $\geq 38.0^{\circ}\text{C}$ / 100.4°F for rectal route. The preferred route for recording temperature in this study will be axillary.

The investigator and designated study staff will assess non-solicited adverse events and will grade them according to Common Terminology Criteria for Adverse Events (CTCAE) Version 5.0.

In the rare case that an adverse event is not graded in the CTCAE, then that event should be graded as follows:

- Grade 1: Mild AE
- Grade 2: Moderate AE
- Grade 3: Severe AE
- Grade 4: Life-threatening or disabling AE
- Grade 5: Death related to AE

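### SAP section 5 prescribes a three-level AE intensity scale that does not match the grades the protocol collects, so its Grade 3 percentages can leave out some severe events

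*SAP*

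**What the plan says.** Near its end, SAP section 5 announces: "The following definitions will be used for clinical adverse events in this report". It continues: "The intensity should be assigned to one of the following categories". Three categories follow: mild, moderate, and a top level worded "3 (severe) = An AE which prevents normal, everyday activities". The SAP adds that intensity and seriousness are different things, since "both AEs and SAEs can be assessed as Grade 3".

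Protocol Appendix B 1.5.1 collects intensity on two other scales.

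- **Self-assessment, Grades 0 to 4.** Grade 3 is an event that "prevents normal daily activities, and/or requires visits with a medical professional". Grade 4 is one that "precipitates ER visit or hospitalization (these are, of course, also SAEs; Serious Adverse Effects").
- **Non-solicited events.** The investigator and designated staff "will grade them according to Common Terminology Criteria for Adverse Events (CTCAE) Version 5.0". Events not graded in CTCAE go on a five-grade fallback that continues above severe: "Grade 4: Life-threatening or disabling AE", then Grade 5 for death.

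SAP section 5 asks for Grade 3 percentages with exact 95% intervals, by participant and by dose, for all AEs and for vaccine-related AEs. It also asks for Grade 3 tabulations of each solicited local AE, each solicited general AE (any and related) and unsolicited AEs (any and causally related). Protocol Appendix B 1.6.1 has the same tabulations. Fever has its own Grade 3 cut-off, above 39.5°C, in both documents.

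**The concern.** The SAP's reporting scale is not the scale on which the data will arrive. Nothing converts one to the other, and nothing says whether Grade 3 means exactly 3, or 3 and above. An analyst can proceed in two ways, and each falls short of the natural meaning of a severe-event rate.

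- **Use the collected grades and count Grade 3 literally.** A participant whose only severe event was Grade 4 or 5 is not in the Grade 3 percentage, so the row excludes the worst grades.
- **Re-grade on the SAP's three levels.** The worst events now fall in the top level. But a self-assessed event that led to a medical visit while only altering activities drops from Grade 3 to moderate.

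Two competent analysts could therefore fill the same row with different participants. Safety is the primary objective and the trial is open-label, so this choice should not be left until the data are seen.

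**Working it through.** The documents give no severe-event rate to reproduce. The check is a comparison of the scales, followed by an illustration of size.

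**Step 1. Classify self-assessed events on both scales** (protocol Appendix B 1.5.1 against SAP section 5).

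| Self-assessed event | Protocol grade | SAP level |
|---|---|---|
| No effect on activities | 1 | 1 |
| Activities altered, no medical visit | 2 | 2 |
| Medical visit, activities altered but not prevented | 3 | 2 |
| Activities prevented | 3 | 3 |
| ER visit or hospitalisation | 4 | 3 if activities are prevented |

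The scales part company in the third and fifth rows. The SAP's top level mentions corrective therapy, but only as an example of what an activity-preventing event would entail, so it does not bring the third row into level 3.

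**Step 2. Unsolicited events.** The fallback scale has Grades 4 and 5, which have no level of their own in the SAP. The medical-visit and hospitalisation criteria belong to the self-assessment scale only, so no third-row difference is claimed for CTCAE-graded events.

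**Step 3. Size per participant.** Arms 1 and 2 have 50 participants each (protocol B6.1). One omitted participant changes the arm's percentage by 1/50 = 2 points, and the pooled vaccinated percentage by 1/100 = 1 point.

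**Step 4. Illustration.** Let T be the number of participants in an arm of 50 with an event of Grade 3 or higher on the protocol scales, and k the number left out under one of the two approaches. The reported rate is (T − k)/50. The exact (Clopper-Pearson) 95% limits for x of n are the 2.5% quantile of Beta(x, n − x + 1) and the 97.5% quantile of Beta(x + 1, n − x). T and k are assumptions.

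| T | k = 0 | k = 1 | k = 2 |
|---|---|---|---|
| 2 | 4% | 2% | 0% |
| 4 | 8% (2.2 to 19.2) | 6% (1.3 to 16.5) | 4% (0.5 to 13.7) |
| 6 | 12% | 10% | 8% |

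Pooled over 100 vaccinated participants, 4 events against 3 gives 4% (1.1 to 9.9) against 3% (0.6 to 8.5).

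The table applies to either approach, but k counts different people in each: those with only Grade 4 or 5 events under the literal count, and those with only medical-visit events under the SAP scale. The two losses are alternatives and must not be added. If no such participants occur, k = 0 and the percentages agree.

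**The case against.** The strongest reply is that the SAP does name its scale. It says which definitions the report will use, level 3 is the top category, and SAEs may be assessed at it, so on the SAP's own terms the worst events are inside the severe row. That stands as the better textual reading of the SAP, and it would be wrong to say that no scale is specified. But the SAP does not say who re-grades the collected data or by what rule. A literal count of collected Grade 3 therefore remains possible in practice, and applying the SAP scale still moves the medical-visit events to moderate.

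Three further points also stand, and they limit the consequence.

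- **Narrow outputs.** The primary endpoints in protocol B6.3.1 carry no grade threshold, the safety outcomes in SAP 3.2 are SAEs, and the summary safety table in SAP section 5 has no Grade 3 row. No test or decision rule uses the Grade 3 percentages.
- **Other tabulations.** Solicited general AEs that led to a medical visit are tabulated separately. If collected grades are used, Grades 4 and 5 also appear in the summaries by group and severity.
- **Assumed size.** The documents give no severe-event rate, and the protocol expects safety events to be rare.

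A reader might go further and infer that serious events would disappear from the report. The documents do not support that: every event stays in the any-AE rows, and the protocol treats self-assessed Grade 4 events as SAEs, which are tabulated in their own right. A reader might also infer that redness, swelling and bruising cannot be graded because they are recorded in millimetres and no cut-offs are visible. That is not established either, since cut-offs may be in the diary card or the SAP appendix, neither of which is in the text available.

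**Conclusion.** Minor; wrong as written. The stated three-level scale does not fit the grades being collected, and no mapping is given. The consequence is a severe-AE percentage that may be too low, by 2 points for each affected participant in a 50-person arm and by nothing if there are none. It is probably small, because it needs participants whose only severe event is of the affected kind. The harm is limited to descriptive Grade 3 tabulations.

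The mismatch itself rests on the text of SAP section 5 and protocol Appendix B 1.5.1 alone. The illustrated rates rest on assumed event counts. Fever is unaffected because it has its own cut-off, and laboratory values are outside the point because they use a separate toxicity table.

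**What to change.** Change SAP section 5 only:

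1. Replace the three-level list with the protocol 1.5.1 scales: the 0 to 4 self-assessment scale for solicited AEs recorded by grade, and CTCAE v5.0 with the fallback scale for unsolicited AEs.
2. Keep the existing Grade 3 fever cut-off above 39.5°C.
3. Wherever the SAP says Grade 3, tabulate Grade 3 or higher, including the related subsets.

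The summaries already planned by group and severity will then show Grades 4 and 5 at their own level, so no extra table is needed.

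The cost is SAP wording before database lock. No new data are required, and no protocol amendment is needed because the SAP can state how the grades are counted. The one downside is that severe-AE percentages may look slightly less favourable.
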